#### **11.4.1.3 Efficacy Analyses**

##### **Primary Efficacy Endpoint**

The change from baseline to Week 52 in LIC will be compared between the two treatment groups using an analysis of covariance (ANCOVA) model, including treatment variable as the main factor and total transfusional iron input during the study and baseline LIC as covariates. The 95% confidence interval (CI) of the difference (deferiprone minus deferoxamine) in change of LIC from baseline to Week 52 between the two treatment groups will be computed. For the demonstration of non-inferiority, the upper limit of the 95% CI should be no more than 2 mg/g dw.

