7.1 Primary Efficacy Endpoint

Primary efficacy endpoint is the change from baseline to Week 52 in LIC. Primary efficacy endpoint will be compared between the two treatment groups using an analysis of covariance (ANCOVA) model including treatment variable as the main factor, and overall average transfusional iron input during the study, baseline LIC, and stratification factors (disease category and transfusional iron input in the 3 months prior to baseline) as covariates. The 96.01% $(1 - \alpha)$, where $\alpha = 0.0399$ based on the Pocock’s α spending function for interim analysis) confidence interval (CI) of the difference (Ferriprox minus deferoxamine) in change of LIC from baseline to Week 52 (i.e., Week 52 minus baseline) between the two treatment groups

will be computed. For the demonstration of non-inferiority, the upper limit of the 96.01% CI should be no more than 2 mg/g dw.

The following SAS codes of MIXED procedure will be used to produce the differences in Least Squares (LS) Mean of change in LIC at Month 6 and Month 12 between Ferriprox and deferoxamine groups and the corresponding 96.01% confidence intervals. In the mixed model, AR (1) (autoregressive of order 1) will be used for the covariance structure, and Kenward and Roger's method will be used to estimate the denominator degrees of freedom (SAS model statement option, DDFM = KR).

```

proc mixed data=LIC;
  class patient treat disease prior_iron month
  model LIC_change = treat overall_iron base_LIC disease prior_iron
    month treat*month / noint solution ddfm=kr;
  repeated month / subject=patient(treat) type=ar(1);
  lsmeans treat*month;
  estimate 'Ferriprox - Deferoxamine at Month 6' treat -1 1
    treat*month -1 0 1 0 / cl alpha=0.0399;
  estimate 'Ferriprox - Deferoxamine at Month 12' treat -1 1
    treat*month 0 -1 0 1 / cl alpha=0.0399;
run;

```

Definition of the variables in the statistical model:

LIC_change : Change in LIC from baseline to Week 5
 treat : Ferriprox or Deferoxamine
 month : Duration of treatment in month
 overall_iron : Overall total transfusional iron input (mg/kg/day) during the study
 base_LIC : LIC at baseline
 disease : Sickle cell disease or other anemias
 prior_iron : transfusional iron input in 3 months prior to baseline (≤ 0.3 mg/kg/day or > 0.3 mg/kg/day)

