7.2 Secondary Efficacy Endpoints

- Change from baseline to Week 52 in patient-reported quality of life (SF-36 or Child Health Questionnaire);
- Change from baseline to Week 52 in cardiac MRI T2*;
- Change from baseline to Week 52 in serum ferritin.
- Detailed information on the statistical analyses of the SF-36 or CHQ data is in a separate SAP prepared by QualityMetric Inc..
- The changes from baseline to Week 52 in cardiac MRI T2* and serum ferritin will be compared between the two treatment groups, using an ANCOVA model including treatment variable as the

main factor, and overall average transfusional iron input during the study, baseline cardiac MRI T2* or serum ferritin, and stratification factors (disease category and transfusional iron input in the 3 months prior to baseline) as covariates. As with LIC, the 96.01% CI of the difference between the two treatment groups will be computed for both cardiac MRI T2* and serum ferritin. The cardiac MRI T2* data will be log-transformed before any statistical evaluation. Since cardiac MRI T2* will be measured at baseline, Week 26, and Week 52 as with LIC, the SAS codes for LIC data, with the exception of baseline MRI T2* instead of baseline LIC being included as the covariate, will be used for cardiac MRI T2* data as well.

- The following SAS codes of MIXED procedure will be used to produce the differences in Least Squares (LS) Mean of change in serum ferritin at Months 3, 6, 9, and 12 between Ferriprox and deferoxamine groups and the corresponding 96.01% confidence intervals.

```
proc mixed data=SF;
  class patient treat disease prior_iron month;
  model SF_change = treat overall_iron base_SF disease prior_iron
    month treat*month /
    noint solution ddfm=kr;
  repeated month / subject=patient(treat) type=ar(1);
  lsmeans treat*month;
  estimate 'Ferriprox - Deferoxamine at Month 3' treat -1 1
    treat*month -1 0 0 0 1 0 0 0 / cl alpha=0.0399;
  estimate 'Ferriprox - Deferoxamine at Month 6' treat -1 1
    treat*month 0 -1 0 0 0 1 0 0 / cl alpha=0.0399;
  estimate 'Ferriprox - Deferoxamine at Month 9' treat -1 1
    treat*month 0 0 -1 0 0 0 1 0 / cl alpha=0.0399;
  estimate 'Ferriprox - Deferoxamine at Month 12' treat -1 1
    treat*month 0 0 0 -1 0 0 0 1 / cl alpha=0.0399;
run;
```

Definition of the variables in the statistical model:

SF_change : Change in SF from baseline to Week 5
 treat : Ferriprox or Deferoxamine
 month : Duration of treatment in month

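### The MIXED code gives baseline LIC one slope for Months 6 and 12, so the Month 12 contrast can differ slightly from the Week 52 ANCOVA that the text describes

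*SAP*

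**What the plan says.** Protocol 11.4.1.3 specifies an ANCOVA of the change in LIC from baseline to Week 52, "including treatment variable as the main factor and total transfusional iron input during the study and baseline LIC as covariates". SAP 7.1 keeps that description: "Primary efficacy endpoint will be compared between the two treatment groups using an analysis of covariance (ANCOVA) model", now with the two stratification factors added as covariates. SAP 7.2 describes the Week 52 changes in cardiac T2* and ferritin in the same way.

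The SAS code in SAP 7.1 is a repeated-measures model on the Month 6 and Month 12 changes. Its fixed effects are "model LIC_change = treat overall_iron base_LIC disease prior_iron", continued by "month treat*month / noint solution ddfm=kr". Treatment is the only term crossed with month. The covariance is AR(1). The Month 12 ESTIMATE statement, "treat*month 0 -1 0 1 / cl alpha=0.0399", gives the interval that is read against 2 mg/g.

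SAP 7.2 reuses this code for cardiac T2*, with baseline T2* as covariate. The ferritin model over Months 3, 6, 9 and 12 has the same form: "model SF_change = treat overall_iron base_SF disease prior_iron".

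**The concern.** An ANCOVA of the Week 52 change uses Week 52 data only, so its baseline coefficient is the Week 52 slope. In the code, the baseline coefficient is a compromise over all visits. If the slopes differ, the Month 12 contrast is adjusted with the wrong one, and part of any baseline difference between the arms stays in the estimate.

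Some chance difference is to be expected. Eligible baseline LIC runs from above 7 to 30 mg/g (Protocol 4.2 and 4.3), and randomisation is stratified by disease category and prior iron input, not by baseline LIC (Protocol 4.9). At stake are a small shift in the non-inferiority estimate, a small loss of precision, and two candidate primary estimates where the plan should have one.

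**Working it through.** **Inputs from the documents.** Interim numbers are 142 and 71 (SAP sample-size text). The SD of change is 4 mg/g (Protocol 11.2.4 and Appendix 18.4), the margin is 2 mg/g, and two-sided alpha is 0.0399 (SAP 3.7).

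**The plan's own figures.**
- Alpha: 0.05 × ln(1 + 1.718 × 0.71) = 0.0399, as stated.
- Power for 79/158 with SD 4, margin 2 and one-sided 0.025: 0.951 by noncentral t, against the stated 0.95017.

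Both reproduce. The documents give no baseline slope at either visit and no baseline SD, so those are assumed below.

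**Scale of the decision.** SE = 4 × √(1/142 + 1/71) = 0.58 mg/g. The 96.01% interval has a half-width of about 1.20 mg/g.

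**Residual in the contrast.** With two visits, equal variance and complete data, the pooled slope is (b6 + b12)/2. SAP section 5 fills Month 12 by LOCF or worst value, so near-complete data is a fair approximation. With D = deferiprone minus deferoxamine baseline mean, the Month 12 contrast retains

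[b12 − (b6 + b12)/2] × D = (b12 − b6)/2 × D.

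**Size of D.** For an assumed baseline SD of 4, 5.5 or 7, one standard error of D is SD × √(1/142 + 1/71) = 0.58, 0.80 or 1.02 mg/g.

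**Slopes.** The only related figures are the deferoxamine reductions of 4.0 and 4.5 mg/g in the >7–14 and >14 bands (Protocol 11.2.4). With assumed midpoints of 10.5 and 22, b12 ≈ −0.5/11.5 = −0.043. This is rough, because the two bands also received different doses. The other rows below are assumptions. The simulated column is the mean difference between the SAP model (REML) and a Week 52 ANCOVA with the same covariates, over 1,000 trials per row with SD 4, correlation 0.6 and baseline SD 5.5.

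| b6 / b12 | D | (b12 − b6)/2 × D | Simulated | Slope used: SAP model v Week 52 ANCOVA |
|---|---|---|---|---|
| −0.022 / −0.043 | 1 | −0.011 | −0.010 | −0.029 v −0.040 |
| −0.15 / −0.30 | 1 | −0.075 | −0.076 | −0.224 v −0.299 |
| −0.15 / −0.30 | 2 | −0.150 | −0.150 | −0.226 v −0.301 |
| −0.25 / −0.50 | 1 | −0.125 | −0.125 | −0.377 v −0.503 |
| −0.30 / −0.15 | 1 | +0.075 | +0.073 | −0.225 v −0.149 |
| −0.15 / −0.30 | not imposed | 0 on average | +0.005 | −0.221 v −0.297 |

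Equal slopes give zero. An extreme pair, 0 / −0.50, would give −0.25 mg/g at D = 1.

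**Precision.** A separate simulation (4,000 trials per setting, Month 6 slope half the Month 12 slope, same SDs and correlation) gives variance ratios of 1.00, 1.01, 1.03 and 1.04 against the Week 52 ANCOVA, for Month 12 slopes of −0.2, −0.4, −0.5 and −0.6. At worst the interval widens by √1.04 − 1 = 2.0%, or about 0.024 mg/g on the 1.20 half-width.

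**Ferritin.** If the slope grows linearly with time and the four visits count equally, the common slope is (3 + 6 + 9 + 12)/4 ÷ 12 = 62.5% of the Month 12 slope.

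**The case against.** **Direction.** A reader might infer that the Month 12 contrast is under-corrected for baseline. The documents do not support that as a general statement. It needs a realised imbalance and a steeper slope at Month 12 than at Month 6. Change is zero at time zero, so a slope that builds up with time on drug is plausible, but no passage says so. Error in the baseline measurement adds the same slope at every visit, and LOCF pulls the two slopes together. A flattening slope gives over-correction. This objection stands.

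**Text against code.** SAP 7.1 itself names the MIXED code as the way to obtain the Month 6 and Month 12 differences, and SAP 14.2.1 labels the output as ANCOVA at each follow-up. The text nowhere promises visit-specific slopes in so many words. That softens the contradiction but does not remove it: an ANCOVA of the Week 52 change has no Month 6 data with which to share a slope.

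**Completeness of the remedy.** A baseline-by-month term leaves common coefficients for on-study iron, disease and prior iron, and AR(1) still assumes one variance for both visits. This is correct. The variance assumption is a separate matter that the term does not touch.

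**LS-mean weighting.** The statement "lsmeans treat*month" has no observed-margins option, so each printed arm mean weights sickle cell disease and other anemias equally, although 178/213 = 83.6% have sickle cell disease. A reader might infer that this distorts the non-inferiority result. It does not. With no treatment-by-disease term, both arm means move by 0.336 (0.836 − 0.5) times the disease effect, and the difference is unchanged. The ESTIMATE contrasts carry no disease coefficient. The SAP also reports observed arm means (Table 14.2.1.2) and results by disease (7.4 and 14.2). The weighting is an optional reporting choice.

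**Conclusion.** The point holds as a minor mismatch between the described analysis and the code. One baseline slope is imposed on all visits, so the Month 12 estimate equals the baseline-adjusted Week 52 estimate only if the slopes agree or the arms happen to balance. For LIC the discrepancy is (b12 − b6)/2 times the imbalance: about 0.01 to 0.125 mg/g per 1 mg/g under the assumed slopes, in either direction, with 0 to 4% more variance. The expected bias over randomisations is zero.

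Against an SE of 0.58 and a margin of 2 mg/g, this could change the conclusion only if the upper limit fell very close to 2. It is not evidence that the non-inferiority test is invalid. The sizes rest on assumed slopes and an assumed baseline SD. That the code has a single slope does not rest on any assumption.

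**What to change.** Before database lock, add `base_LIC*month` to the LIC model, `base_SF*month` to the ferritin model and baseline T2* by month to the T2* model, so that each Month 12 contrast uses the Month 12 baseline slope. The cost is one degree of freedom per added visit: one each for LIC and T2*, three for ferritin. If the slopes turn out equal, almost nothing is lost.

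Alternatively, fit the described ANCOVA to the Week 52 change alone and keep the repeated-measures model as supportive. That removes the text–code mismatch completely, including for the other covariates. The LSMEANS statement does not need to change.

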### 11.2.4 Determination of Sample Size

Three hundred (300) male and female patients will be enrolled into the study. In a randomized study of two iron chelators for the treatment of iron overload in patients with sickle cell disease (Vichinsky et al., 2006), mean  $\pm$ SD reductions of  $4.0 \pm 1.5$  mg/g dw and  $4.5 \pm 2.0$  mg/g dw were observed (Figure 1 of the article, numerical values obtained from the authors) in patients from the baseline LIC categories of  $>7$ - $14$  mg/g dw or  $>14$  mg/g dw after they were treated with 35-50 mg/kg or  $\geq 50$  mg/kg of deferoxamine respectively, for 52 weeks. Assuming the same mean reduction in LIC for deferiprone but a higher SD of  $\pm 4.0$  mg/g dw for both treatments due to possibly higher variability associated with MRI measurement, the sample size of 300, with  $>80\%$  being patients with sickle cell disease, will provide over 95% power for demonstrating non-inferiority of deferiprone to deferoxamine in patients with sickle cell disease.

The sample size estimate is based on a non-inferiority margin of 2 mg/g dw for the reduction of LIC and an alpha of 0.05, two-sided (or an alpha of 0.025, one-sided, Appendix 18.5). It has been reported that in a typical patient with thalassemia major, the LIC could increase by 5 mg/g dw after 1 year without chelation therapy. As the cause of iron overload is the same in thalassemia and sickle cell disease, the same increase in LIC may be expected in patients with sickle cell disease who are transfused at the same rate and not treated with a chelator. Hence, the difference in reduction of LIC between deferoxamine therapy and a placebo (effect size) can be estimated to be 9 (i.e., 4 – (-5)) mg/g dw. This means that the non-inferiority margin of 2 mg/g dw would be about 20% of the effect size.

With the enrolment of 300 patients, there is also greater than 99% chance (power) of occurrence of at least 1 adverse event with an anticipated incidence rate of 2%, or greater than 95% chance for an anticipated incidence rate as low as 1%.

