However, patient's recruitment in this study has proceeded at a very slow pace and despite all our efforts over the past 4 years, the goal of enrolling a total of 300 patients has not been reached. A total of 213 patients (142 patients for Ferriprox and 71 patients for deferoxamine) are projected to have either completed the study or been withdrawn from the study by November 30, 2018. An interim analysis is planned to be performed on the data of these 213 patients. Based on the same values of non-inferiority margin and SD of the LIC measurement, but an α level of 0.0399, two-sided (Pocock's α spending method, see section 3.7 for details), this sample size (213 patients) will provide 89% power to demonstrate non-inferiority of Ferriprox to deferoxamine in this interim analysis, assuming no real difference in efficacy between the two treatments. For the subgroup analysis of only patients with sickle cell disease, the power will be 82% as there are 178 SCD patients (119 patients for Ferriprox and 59 patients for deferoxamine), which is approximately 84% of 213 patients. With the safety data of 213 patients, there is 98% chance (power) of occurrence of at least 1 SAE with an anticipated incidence rate of 2%, or 88% chance for an anticipated incidence rate of as low as 1%.

During this interim analysis, while patient enrollment has been put on hold, there will still be 17 patients who are on-going with their assigned drug treatment. All are projected to have completed the study by October, 2019. If the results of the interim analysis lead to the conclusion of non-inferiority of Ferriprox to deferoxamine, considerations will be given on early termination of the study, to avoid unnecessary exposure of patients to a clinical trial that has reached its objectives. The data from those patients up to the time of

study closure will be added to the interim dataset for the final statistical analysis of the study based on the same statistical analyses in this SAP.

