3.3 Treatment

Baseline Phase:

During the baseline phase, patients who sign an informed consent form will undergo initial screening. On the final day of the baseline phase, patients' eligibility will be determined, based on inclusion/exclusion criteria, and qualified patients will enter the treatment phase.

Treatment Phase:

At the beginning of the treatment phase, patients will be randomized in a 2:1 ratio to receive either deferiprone or deferoxamine. The treatment phase will be 52 weeks in duration.

Deferiprone Treatment Arm:

Patients will be prescribed Ferriprox 500 mg tablets and/or 80 mg/mL oral solution, according to patient preference or product's availability, for administration three times a day (tid). The dose of Ferriprox will be based on the transfusional iron input and the severity of iron overload at baseline, and may be adjusted on the basis of the magnitude of change in iron overload during the study.

Ferriprox 25 mg/kg tid:

Patients with transfusional iron input ≤ 0.3 mg/kg/day in the 3 months prior to baseline

AND

Patients with a baseline measure of iron load of:

- Serum ferritin < 2500 $\mu\text{g/L}$

AND

- LIC < 15 mg/g dry weight

AND

- Cardiac T2* > 20 ms

Ferriprox 33 mg/kg tid:

Patients with a transfusional iron input > 0.3 mg/kg/day in the 3 months prior to baseline

OR

Patients with at least one baseline measure of iron load as follows:

- Serum ferritin ≥ 2500 $\mu\text{g/L}$

OR

- LIC ≥ 15 mg/g dry weight

OR

- Cardiac T2* ≤ 20 ms

Dosing of all patients will be initially at 15 mg/kg tid for 1 week, which will be increased to 20 mg/kg tid in Week 2 and to 25 mg/kg tid in Week 3, which will be the treatment dose for the remainder of the trial, unless a patient meets the 33 mg/kg tid dosing criteria. In that case, the dose of Ferriprox will be increased further to 33 mg/kg tid in Week 4, and this dose will be the treatment dose for the remainder of the trial.

The dose of Ferriprox will also be increased to 33 mg/kg tid at any time during the trial if the mean daily transfusional iron input increases to more than 0.3 mg/kg body weight for at least 3 consecutive months OR at Week 26 if there is less than 10% improvement from baseline to Week 26 in at least one of the measures indicative of iron overload (serum ferritin, cardiac MRI T2* or LIC).

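### The primary LIC model gives both arms one residual variance under 2:1 allocation, so the non-inferiority interval relies on equal SDs; an arm-specific variance is a cheap safeguard

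*SAP*

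**What the plan says.** SAP 7.1 fits the change in LIC at Months 6 and 12 with PROC MIXED. The text states that "AR (1) (autoregressive of order 1) will be used for the covariance structure", and the code line is "repeated month / subject=patient(treat) type=ar(1"). The nesting of patient within treatment only identifies subjects. Without a GROUP= or EMPIRICAL option, both arms share one residual variance and one correlation. Kenward and Roger's "method will be used to estimate the denominator degrees of freedom".

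The decision rule follows directly from this model: "the upper limit of the 96.01% CI should be no more than 2 mg/g dw". The interim analysis uses an alpha "level of 0.0399, two-sided". SAP 3.3 states that "patients will be randomized in a 2:1 ratio to receive either deferiprone or deferoxamine", and the SAP's sample-size text projects the numbers: "A total of 213 patients (142 patients for Ferriprox and 71 patients for deferoxamine").

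Protocol 11.2.4 assumes an SD of 4.0 mg/g dw "for both treatments due to possibly higher variability associated with MRI measurement". The sample-size output in Protocol Appendix 18.4 enters 4.000 for each group. The sensitivity analyses in SAP 7.5 change the imputation and restrict the patient set. None of them lets the variance differ by arm.

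**The concern.** A pooled variance takes about two thirds of its weight from deferiprone, the larger arm. The true variance of the treatment difference depends more on the smaller deferoxamine arm. With equal arms the two nearly coincide even when the SDs differ, but with 2:1 allocation they do not.

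If deferoxamine patients vary more, the interval is too narrow and non-inferiority is declared too often when the true difference sits at the margin. If they vary less, the interval is too wide and power is lost. Kenward-Roger does not correct this, because it adjusts within the covariance structure that was specified. Changing only TYPE= does not help either, since the same matrix is still imposed on both arms.

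**Working it through.** **Inputs.** Margin 2 mg/g dw and the 96.01% interval (SAP 7.1); n = 142 and 71 (SAP sample-size text); SD 4.0 in each arm and true difference 0 (Protocol 11.2.4 and Appendix 18.4). Every unequal SD below is an assumption.

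**The plan's own figures.** Appendix 18.4 reports power 0.95017 for 79 and 158 patients at one-sided 0.025. A noncentral-t calculation gives 0.9509 with a pooled variance and 0.9501 with separate variances, so the figure reproduces. The Pocock spend also reproduces: 0.05 × ln(1 + 1.718 × 0.71) = 0.0399, that is 0.01995 on the non-inferiority side, with critical value 2.055.

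**Formulas** (1 = deferiprone, 2 = deferoxamine; two-sample approximation without covariates):

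- Pooled variance = (141·s1² + 70·s2²) / 211
- Model SE = √[pooled variance × (1/142 + 1/71)]
- True SE = √(s1²/142 + s2²/71)
- One-sided error at the margin = 1 − Φ(2.055 × model SE / true SE)

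**Example, SDs 4 and 5.** Pooled variance = (141 × 16 + 70 × 25)/211 = 18.99. Model SE = 0.633. True SE = √(0.1127 + 0.3521) = 0.682. The ratio is 0.929, and the error is 1 − Φ(1.909) = 0.028.

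| SD deferiprone / deferoxamine | Model SE | True SE | Half-width, model / correct | One-sided error |
|---|---|---|---|---|
| 4 / 4 | 0.581 | 0.581 | 1.19 / 1.19 | 0.020 |
| 4 / 4.25 | 0.594 | 0.606 | 1.22 / 1.24 | 0.022 |
| 4 / 4.5 | 0.607 | 0.631 | 1.25 / 1.30 | 0.024 |
| 4 / 5 | 0.633 | 0.682 | 1.30 / 1.40 | 0.028 |
| 4 / 6 | 0.692 | 0.787 | 1.42 / 1.62 | 0.036 |
| 4 / 3 | 0.538 | 0.489 | 1.10 / 1.01 | 0.012 |
| 6 / 4 | 0.788 | 0.692 | 1.62 / 1.42 | 0.010 |

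In the conservative direction the loss is power. At no true difference and SDs 6/4, power is 71% with the common variance and 80% with the correct one.

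**Role of the allocation.** The same formulas with 107 and 106 patients give 0.020 at both 4/5 and 4/6. For the sickle cell subgroup (119 and 59) they give 0.028 and 0.036, as in the whole trial.

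**Simulation check.** There were 12,000 simulated trials per scenario, with two visits, the SAP's covariates, an assumed between-visit correlation of 0.6 and Satterthwaite degrees of freedom. The common-variance AR(1) model gave 0.020 (4/4), 0.028 (4/5), 0.037 (4/6) and 0.009 (6/4). A Month 12 model with arm-specific variances gave 0.018 to 0.021 throughout.

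**Cost when the SDs are equal.** Power with 142 and 71 patients is 91.4% with the pooled variance and 91.3% with separate variances. The SAP states 89% for this setting, which these inputs do not reproduce. The cost is the difference between the two computed powers and does not depend on that figure.

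**The case against.** The strongest reply is that nothing in the documents shows unequal SDs between the arms. Under the plan's own 4.0 in each arm the interval is exactly right, and a common-variance ANCOVA is the usual default and the protocol's stated method. This stands, and it rules out calling the interval wrong.

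A reader might take the planning study's SDs of 1.5 and 2.0 as evidence of unequal arms. They are not: both are deferoxamine SDs, from different baseline-LIC categories and dose bands. The randomised arms each mix such patients, and the model adjusts for baseline LIC.

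Protocol 11.2.4 attributes the rise to 4.0 to MRI measurement, which would affect both arms alike. On that reading (an inference), the shared variance is 16 − 4 = 12 to 16 − 2.25 = 13.75. Even with 1.5 and 2.0 placed in opposite arms, the SDs would be 3.77 and 4.00, or 4.00 and 4.21. That is a ratio of about 1.05 to 1.06 and an error of about 0.022. The errors of 0.028 and 0.036 therefore need a larger imbalance than the cited figures suggest.

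A reader might also infer a direction from the arms' differing routes and withdrawal rules. The documents do not support one. The neutropenia rules are written for deferiprone, and any spread they add would fall in the larger arm, which is the conservative direction. The worst-value imputation in SAP 5 draws on each arm's own extreme, so it could widen either arm.

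What survives is narrower: the decision interval rests on an equality that the plan neither checks nor tests in a sensitivity analysis, and 2:1 allocation removes the usual protection.

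**Conclusion.** This is a worthwhile low-cost improvement, not an error that the documents demonstrate. The LIC interval is correct if the arms' SDs are equal. If deferoxamine's SD were 6% to 12% higher (4.25 to 4.5 against 4), the one-sided error would be 0.022 to 0.024 against 0.01995. It would reach 0.028 at 25% higher and 0.036 at 50% higher. If deferoxamine were the less variable arm, the test would be conservative (0.012 at 4/3). All these figures rest on assumed SDs and a two-sample approximation supported by simulation.

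The tempting stronger reading, that this trial's false non-inferiority rate is inflated, is not supported: both the SD ratio and its direction are unknown. The point also does not carry over in full to cardiac T2* and ferritin. Their models have the same form, but no margin is set for them, so only the accuracy of their intervals is affected.

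**What to change.** In the SAP 7.1 LIC code, add `group=treat` to the REPEATED statement, keeping the same TYPE= and `ddfm=kr`, and say so in one line of text. Use the same option for the sickle cell subgroup LIC model in SAP 7.4.

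For T2* and ferritin (SAP 7.2) the option is optional. For the non-SCD subgroup, 213 − 178 = 35 patients, or about 23 and 12 by arm, keep the common variance, or state a fallback to it if the model does not converge. A separate variance and correlation from about 12 patients would be poorly estimated.

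The cost is slightly fewer degrees of freedom and, if the SDs are equal, about 0.1 point of power (91.4% to 91.3%).
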